Primary Endpoint for performance included an evaluation of the ability of participants to selfmeasure FHR with the device. Primary Endpoints for usability included an evaluation of the following: success rate of the user's ability to self-select the device in accordance with the label; success rate of the user in independently performing critical and essential tasks (objective measure) and user perspective of success (subjective measure, systematically collected) for critical and essential tasks. The Secondary Endpoint for safety included an evaluation by reporting the incidence and severity of all device related adverse events. The study consisted of a single visit, conducted on one day. Patients were self-selected during the screening process. Usability and performance of the device was evaluated by study personnel.

The feasibility study results were as follows:

- Performance success rate of Fetal Heart Rate detection was 100% (CI 85.2 100.00).
- The Pass/Fail success rate for all the usability critical and essential tasks was 100% in the following domains: 1. Self-Selection, 2. Task Performance: Training Material, Handling the Compass, Performing the Procedure, Performing the Switching Off.
- User Perspective of Success was evaluated by a post tasks questionnaire. Each question was evaluated on a scale from 1 to 5 (1. Strongly disagree; 2. Disagree; 3. Neither agree nor disagree; 4. Agree; 5. Strongly agree). Mean scores were calculated for each question. Results ranged from 4.3 to 5.0, indicating that expectant moms agreed or strongly agreed with the ease of use of the device.
- There were no safety issues or adverse events reported. Post-development testing indicated that the Compass System (now HeraBEATTM) was successful in achieving its per protocol efficacy and safety endpoints, usability and performance measures.

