## 5.6 Schema

Patients will be instructed to monitor their fetus once weekly, using their assigned device, from 20 weeks to 36/37 weeks gestation. Patients using the HeraBEATTM device will have their FHR and MHR data displayed on their App, and uploaded to a HIPPA compliant cloud based server, which can be accessed by the healthcare provider for review (*Appendix B*). Patients using the standard handheld Doppler device will be given a study brochure for recording their weekly data. Patients using the HeraBEATTM device will be instructed to bring their device during their outpatient clinical appointments, for comparison of MHR and FHR during their routine clinic appointments using methods documented in *Appendix E*.

After approximately 8 weeks of monitoring, patients will complete a System Usability Survey (SUS Survey), *Appendix D* to assess ease of use of the device, then crossover to the alternate study product.

Patients who are randomized to HeraBEATTM from 20weeks gestation to 28 weeks gestation will be given the standard fetal Doppler. Patients who are randomized to the standard Fetal Doppler will switch to the HeraBEAT.TM At the conclusion of each patient device use (28 weeks and 36 weeks gestation), participants will complete the System Usability Survey (Appendix D) to assess ease of use of each device.

- 1- Nurse assesses eligibility criteria, ascertains mother's interest, and study coordinator will obtain consent and complete randomization Patients will be given home monitoring equipment after their fetal anatomy sonography is complete, inclusion/exclusion criteria confirmed and Patient Usability Form completed (Appendix C).
- 2- After 8 weeks of use, participants will complete the System Usability Scale (SUS) survey (Appendix D), return the first study device and crossover to the second device. An independent device use assessment (Appendix C) will be assessed by study nursing staff and completed for the second device.
- 3- At the conclusion of 8 weeks of self-monitoring with assigned device, participants will complete the System Usability Scale (SUS) survey to assess ease of use (Appendix D).

Prior to registering study participants, all eligibility criteria will have been met and fully documented. Mothers will be randomized by the study coordinator after completion of standard informed consent for participation in clinical research including permission to use Protected Health information.

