#### 8.0 Data Analysis Plan

The study will be analyzed according to the intention to treat principle, including all mothers randomized to the study in the arm to which they were randomized, regardless of whether they received the intervention assigned.

Baseline characteristics will be reported in the study results with continuous values being reported as means and standard deviations or median interquartile range as appropriate. Categorical values will be reported as counts and proportion. Two sample t-tests or Wilcoxonrank sum test and chi-squared tests or Fishers exact test will be used as appropriate. Any baseline imbalances (p<0.05) will be explored as a possible confounder to adjust for when the outcome measures are analyzed. We will adhere to the CONSORT guidelines to transparently

report study results and ensure that sufficient information is included to allow for assessment of the study's internal and external validity.

Ease of use will be estimated from the System Usability (SUS) validated questionnaire. These data will be analyzed as a two sample t-test prior to cross over. After cross over we will analyze these data using an ANCOVA adjusting for order of medical devices or as a paired t-test as appropriate.

Within the SUS survey, we will also examine trends within individual questions using chi-square tests. Clinical concerns in FHR will be indicated as a FHR less than 110 bpm or greater than 160 bpm. These data will be analyzed as McNemar's test on the association of the study medical devices with the clinical standard of care. Comparing ease of use metrics will be done using an ANCOVA analysis or generalized estimating equation as appropriate adjusting for gestational age. Additional ad-hoc analysis will be performed using standard techniques appropriate for randomized trials, with each outcome compared between study arms using t-tests for continuous outcomes and chi-square tests for dichotomous outcomes. If there are differences in baseline characteristics between the two study groups, these will be accounted for using ANCOVA or regression models which include an indicator for study arm.

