## 8.2 Sample Size

Difference in ease of use between our standard fetal Doppler and HeraBEAT™ device, as measured by the System Usability Survey (SUS) will be the primary outcome. Approximately 1500 – 2000 expectant mothers receive prenatal care in the obstetric department annually. We aim to recruit 50 participants (50 per arm, with cross-over) for a 99.7% power to detect a 10-point difference in SUS, as this accounts for a withdraw / post-randomization exclusion, estimated as high as 10% (assuming a proportion of expectant mothers to withdraw participation after being enrolled or found to not meet criteria after the fact).

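### Single SUS questions are to be examined for trends with an unspecified chi-square test, which on its ordinary reading ignores answer order and, after cross-over, pairing

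*Combined protocol and SAP*

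**What the plan says.** Section 8.0 (Data Analysis Plan) states that "we will also examine trends within individual questions using chi-square tests". It does not say which chi-square test is meant, whether all answer categories are kept, or whether the comparison is between arms before cross-over or between devices over both periods.

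The same section is more specific elsewhere. For total SUS it names a two-sample t-test before cross-over, and an order-adjusted ANCOVA or paired t-test afterwards. It names McNemar's test for clinical concerns in fetal heart rate, and Wilcoxon rank-sum and Fisher's exact tests for baseline data.

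Section 5.6 makes the design paired: at the end of each device period, "participants will complete the System Usability Survey (Appendix D) to assess ease of use of each device". Section 8.2 says that the difference in ease of use, "as measured by the System Usability Survey (SUS) will be the primary outcome", and its only power statement is for that score: "We aim to recruit 50 participants (50 per arm, with cross-over) for a 99.7% power to detect a 10-point difference in SUS". Loss is "estimated as high as 10" percent.

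The supplied text does not include Appendix D, so the answer format of the SUS questions is not visible. Section 4.0 says of the earlier feasibility questionnaire that "Each question was evaluated on a scale from 1 to 5", but that is a different instrument.

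**The concern.** A trend across ordered answers is a directional question. An ordinary chi-square test of device by answer category gives the same p-value if the answer labels are shuffled, so it cannot aim at a direction. A significant result may reflect a wider spread of answers with no shift towards easier or harder. A real shift in one direction is diluted over several degrees of freedom.

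After cross-over there is a second problem. Pooling both periods into one device-by-answer table treats two answers from the same woman as independent. When they are positively correlated, the test is conservative and loses further power.

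At stake is the reading of the single questions. A non-significant question could be taken as evidence that the devices do not differ on that aspect, when the test had little chance of showing a difference.

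**Working it through.** **Inputs**
- From section 8.2: 50 women, up to 10% lost, a 10-point SUS difference. Evaluable women: 50 × 0.9 = 45. With 1:1 allocation (assumed), 25 × 0.9 = 22.5, taken as 22 per arm before cross-over.
- Assumed, because the documents do not state them: five ordered levels, a 0 to 100 total, two-sided alpha 0.05, the 10 points spread evenly over the questions, and three baseline answer distributions. The p<0.05 in section 8.0 applies to baseline imbalance only.
- Item shift: 10/100 = 10% of the range. A five-level item spans 5 − 1 = 4 units, so the shift is 0.1 × 4 = 0.4 units.

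**The plan's own figure.** The stated 99.7% cannot be reproduced forward, because no SD is given. Solving backwards for a paired t-test, with power = P(t(n−1, noncentrality δ√n/σ_d) > t_0.975), gives σ_d of about 13.9 with 45 women (14.7 with 50). Check at 45: 10 × 6.708/13.93 = 4.82; the critical value is about 2.02; Φ(4.82 − 2.02) = Φ(2.80) ≈ 0.997. For two independent groups, the implied SD is about 10.0 with 45 per group. None of this gives a power for a single question.

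**Step 1: why order matters.** A 2 × 5 table has (2 − 1)(5 − 1) = 4 degrees of freedom; a trend test has 1. The 5% critical values are 9.49 and 3.84. For a purely ordered shift the noncentrality is about the same, so a trend test with 50% power corresponds to about 31% for the 4-df test, a loss of 19 points. Likewise 30% becomes 18% (12 points) and 70% becomes 48% (22 points).

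**Step 2: simulation at 45 answers per device, unpaired.** Latent-normal answers, shift solved to give a mean item difference of 0.4, 3,000 replicates.

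| Assumed baseline answers | Pearson, 4 df | Rank-sum, same data | Loss (points) |
|---|---|---|---|
| .05 .10 .20 .40 .25 | 25.9% | 46.3% | 20.4 |
| .10 .20 .30 .25 .15 | 18.8% | 33.5% | 14.7 |
| .03 .12 .30 .35 .20 | 25.9% | 46.6% | 20.7 |

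This is about 15 to 20 points; repeat runs move individual values by a point or two.

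**Step 3: other readings of the sentence**
- Before cross-over only, 22 per arm: a loss of about 9 to 12 points.
- Answers collapsed to agree or not, 45 per device: 1 df, a loss of about 8 to 12 points against the rank test.
- Chi-square test for trend: power matches the rank test, so the loss is about zero.

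**Step 4: pairing.** The variance of a within-woman difference is 2σ²(1 − ρ), while the unpaired test works as if it were 2σ². At ρ = 0.5 that overstates the variance twofold. At the 0.4-unit shift with 45 women and ρ = 0.5, the unpaired Pearson test has about 14 to 21% power and the signed-rank test about 55 to 71%, a gap of 55 − 14 = 41 to 71 − 21 = 50 points.

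Not all of that gap comes from order. With symmetric answers (.1 .2 .4 .2 .1), a latent shift of 0.4 SD and ρ = 0.5, power is 17.6% for Pearson, 41.1% for the unpaired trend test and 68.2% for a paired test. So 41.1 − 17.6 = 23.5 points come from order and 68.2 − 41.1 = 27.1 from pairing. With no device effect and ρ = 0.5, the unpaired Pearson test rejects in only about 3% of trials, and the unpaired trend test in about 1%.

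**Step 5: sparse cells.** At 45 per device, 87% to 99% of simulated tables had an expected count below 5. At 22 per arm, over 99% did. Section 8.0 offers Fisher's exact test for baseline data but not for these questions.

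**The case against.** The strongest reply is that the sentence never says Pearson. With the word trends in it, it could mean a chi-square test for trend, which uses the order and loses nothing on that score. It could also mean collapsed answers, since section 8.0 elsewhere links chi-square tests to two-valued outcomes. This stands: a reader might infer that the plan certainly discards answer order, but the text supports that only as the ordinary reading. It does not make the sentence adequate, because these tests can disagree on the same data, and an unpaired trend test after cross-over would still ignore pairing.

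The answer format is also unseen. Section 5.9.2 says the survey covers safety concerns and whether the device was useful, so some questions may be yes/no. This stands too, and it rules out a blanket ban on nominal tests.

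Third, an unpaired rank test reaches only about 34 to 47% in the main setting, so it too would miss most such shifts. That is correct: using the order alone does not make single questions well powered, and much of the further gain comes from pairing.

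Finally, no power target or stated decision rests on single questions, and section 8.0 also plans ANCOVA or GEE for ease-of-use metrics. The first part stands and limits the importance. The second does not settle the matter, because the sentence on individual questions names only chi-square.

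**Conclusion.** The point holds in conditional form. On the ordinary reading, the named test does not match an ordered, paired question. The loss from ignoring order is about 15 to 20 points of power at 45 per device and about 9 to 12 at 22 per arm. These figures rest on five ordered levels, an even spread of the 10-point difference, the assumed answer distributions and alpha of 0.05. Over a wider grid of distributions, sample sizes and cumulative odds ratios from 1.5 to 5, the loss runs from about 4 to 25 points. Ignoring pairing adds to it when a woman's two answers are correlated.

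Two stronger readings are not supported. A reader might take 15 to 20 points as a fixed property of the plan, but the documents give no item-level effect, answer distribution or SD from which to derive it. A reader might also infer that the trial's main conclusion is at risk. It is not: total SUS is the primary outcome and has its own two-sample, paired or order-adjusted analysis. The label is a cheap improvement.

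**What to change.** Replace the sentence in section 8.0 with:

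> Individual SUS questions with ordered answers will be compared between devices on their full scale: Wilcoxon rank-sum (or chi-square test for trend) before cross-over, and Wilcoxon signed-rank on within-woman differences, or an ordinal GEE model with device and period, after cross-over. Any yes/no question will use McNemar's test on paired answers. Question-level results are exploratory and will be reported with 95% CIs.

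The cost is a few lines of SAP text and slightly different code, with no new data or participants. There are small downsides. Ordinal tests are less sensitive to a change in spread without a shift, which is not the stated question. The signed-rank test does not itself adjust for period; the GEE model does, but it may be unstable with about 45 women and sparse categories. In that case the signed-rank test should be used, and the SAP should say so in advance.

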#### **1.0 Specific Aims**

The coronavirus disease 2019 (COVID-19) global pandemic rapidly changed the standard model of prenatal care in the United States. In response to this pandemic, the Society for Maternal Fetal Medicine (SMFM) and the American College of Obstetricians and Gynecologists (ACOG) recommended integrating telehealth services as appropriate, limiting face-to-face patient contact if clinically possible, and considering alternative methods of providing obstetric care, to decrease the risk of COVID-19 exposure.

Evidence for integrating home monitoring devices and telehealth services for the provision of prenatal care is limited Innovative options for home monitoring of fetal well-being, as a component of virtual or a hybrid prenatal care model is equally negligible. While a few studies have focused on home monitoring of maternal blood pressure, capillary blood glucose, and contraction patterns, few have investigated maternal home monitoring of fetal heart rate, as a component of virtual or hybrid prenatal care.

In addressing this gap, HeraMED designed and tested a medical grade, smartphone fetal heart rate monitor - HeraBEAT USATM ((HeraBEATTM) - for self-administration at home, under clinical guidance of an obstetric provider.

We propose that HeraBEATTM self-administered at home by pregnant women, under clinical guidance, will result in accurate monitoring of fetal heart rate, provide peace of mind to patients between prenatal appointments, and enhance the overall prenatal experience of pregnant women.

To evaluate the functionality and acceptability of HeraBEATTM we plan to:

- 1. Assess the functionality of HeraBEAT™ self-administered by pregnant women.
  - a. Hypothesis: Pregnant women will demonstrate a working knowledge on use of the device, when observed by medical staff, will trouble-shoot appropriately and will rate the device instructions as easy to follow.
  - b. Hypothesis: Pregnant women will appropriately self-monitor FHR successfully at home, transmit the data to caregivers, and use the device as prescribed.
- 2. Assess the acceptability of HeraBEATTM when self-administered by a pregnant women in the home by assessing the following
  - a. Hypothesis: Pregnant women will rate the device as easy to use, easy to interpret, and have minimal disruption in lifestyle as measured by a standardized survey.

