#### **3.3 Investigational Device**

The 'HeraBEAT USATM (HeraBEATTM) is a wireless Smart Fetal Ultrasound Doppler measuring device designed to be self-administered by pregnant women. The 'HeraBEATTM' device safety and performance claims allow continuous and accurate measurement of fetal heart rate (FHR) and maternal heart rate (MHR) throughout the pregnancy starting at 12 weeks gestation. This study shall evaluate the device performance starting at 20 weeks gestation.

Technologically, HeraBEATTM is similar to other FHR devices currently on the market in terms of device usage but differ by design in its interface. The HeraBEATTM device uses a smartphone-based interface, with real time instructions for localizing FHR. The device also measures the maternal heart rate (MHR) and uses this in its algorithm. This is primarily in order to overcome common lay person usage errors such as confusion between MHR and FHR or difficulties locating the FHR due to lack of experience. The data obtained from the device is uploaded to a secure HIPAA compliant cloud-based server for medical providers to review. The intended use, indication for use and contraindications are similar to current medical grade handheld fetal Doppler devices.

The specifications for the HeraBEATTM are:

- The device will measure fetal heart rate in range of 50-240 BPM.
- The device will measure fetal heart rate with accuracy of  $\pm 2$  BPM.
- The device will measure fetal heart rate with resolution of 1 BPM.
- FHR value is calculated and displayed every 1 second.
- Device measures FHR and MHR starting at 12 week gestation.
- The device will measure maternal heart rate in range of 45-240 BPM.
- The device will measure maternal heart rate with accuracy of  $\pm 2\%$  or 1 BPM, whichever is greater.
- The device will measure maternal heart rate with resolution of 1 BPM.

• MHR value is calculated and displayed every 1 second.

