# Table 1: 'HeraBEATTM', system specification

FHR Performance	FHR Measuring Range; Accuracy; Resolution	50 to 240 BPM; ±2BPM; 1 BPM		
	MHR Measuring Range; Accuracy; Resolution	45 to 240 BPM; ±2% or 1 BPM, whichever is greater; 1 BPM		
Auto Acquisition	stop	5 minutes of successful measurement		
Recommended Ultrasound Transmission Gel		Aquasonic 100 Ultrasound Transmission Gel, by Parker Laboratories.		
Power consumption	on	< 2 W		
Rechargeable	Nominal Capacity	3.7VDC, 1250 mAh		
Li-ion Battery	Continuous Work Time	4 hours (with a new battery)		
	Power Input	5 V DC, >0.3A		
	Charge Time	4 hours		
Ultrasound (NEMA/FDA)	Nominal Frequency	2 MHz ±10%		
	Ultrasonic Output Power (P)	70mW		
	Peak rarefactional pressure ( p r )	0.03 MPa		
	Ultrasonic Output Intensity (I sata )	$\leq 20 \text{mW/cm}^2$		
	Mechanical Index (MI)	0.02		
	Thermal index (TIS; TIB)	0.26; 0.7		
	Measurement Mode	Continuous Wave Ultrasound Doppler		
	Effective Radiating Area of Transducer	$4.9\pm0.5 \text{ cm}^2$		
BLE specification	frequency band of transmission	
 
2.4 – 2.5 GHz
 
Channels (2MHZ spacing)
 
3 Advertising channels @ 2402, 2426
 
2480Mh
 
36 data channels
 
		
	frequency characteristics of the modulation	DSSS: GFSK (modulation index = 0.5)		
	Maximum RF Input	-10 dBm		
	Typical Receive Sensitivity	-94 dBm		

Maximum RF Tx Output	+4 dBm
Power	

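### Section 8.0 compares device and clinic FHR only through a 110/160 bpm flag with McNemar's test and states no analysis of MHR, so some constant errors of 10 to 20 bpm could go unseen

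*Combined protocol and SAP*

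**What the plan says.** All references are to the combined protocol and SAP.

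- **Proposition.** Section 1.0 proposes that guided home use "will result in accurate monitoring of fetal heart rate".
- **Device specification.** Table 1 gives "50 to 240 BPM; ±2BPM; 1 BPM" for FHR and "45 to 240 BPM; ±2% or 1 BPM, whichever is greater; 1 BPM" for MHR (range, accuracy, resolution). Section 3.3 says MHR enters the device's algorithm mainly to guard against "confusion between MHR and FHR or difficulties locating the FHR due to lack of experience".
- **Data collected.** In Section 5.6, HeraBEAT users bring the device to their appointments "for comparison of MHR and FHR during their routine clinic appointments using methods documented in" Appendix E.
- **Analysis of FHR.** Section 8.0 states: "Clinical concerns in FHR will be indicated as a FHR less than 110 bpm or greater than 160 bpm". The next sentence assigns McNemar's test, comparing the study devices with standard clinical care. The only paired device and clinic readings described are those of Section 5.6, so I take the test to apply to them.
- **Analysis of MHR.** Section 8.0 does not mention it. Section 5.9.3 uses MHR only in counting how often women make recordings.
- **Ad hoc analyses.** The t-tests and chi-square tests at the end of Section 8.0 compare study arms. They do not compare device with clinic within a woman.

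**The concern.** A pair of numerical readings can show whether a device reads high or low, and by how much. The flag keeps only whether each reading lies inside a wide band. Two readings that differ greatly count as agreement if both fall inside it.

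McNemar's test adds a second limitation. It asks whether device and clinic raise the flag equally often. If the device misses some flags and raises as many false ones, the test sees no difference. A non-significant result is therefore not evidence that paired readings agree, and this holds for any sample size.

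At stake is what the report can say about the accuracy proposed in Section 1.0. A finding of no difference in flags could be true of a device with a constant error of 10 bpm or more. For MHR, on which the device relies to avoid confusing mother and fetus, Section 8.0 would yield no statement at all.

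**Working it through.** **1. Stated figure.** The plan gives none for FHR or MHR accuracy. The 99.7% power in Section 8.2 concerns a 10-point SUS difference and has no bearing here.

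**2. Band arithmetic (no assumptions).** With limits of 110 and 160, the unflagged band is 160 − 110 = 50 bpm. An error of size *e* in either direction leaves both readings unflagged when the reference lies between 110 + *e* and 160 − *e*.

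| Error *e* | Reference values where it is invisible both ways | Width, 50 − 2*e* | Width for one direction only, 50 − *e* |
|---|---|---|---|
| 10 bpm | 120 to 150 | 30 | 40 |
| 15 bpm | 125 to 145 | 20 | 35 |
| 20 bpm | 130 to 140 | 10 | 30 |

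Example: clinic 130 and device 150 count as agreement, although the gap of 20 bpm is ten times the 2 bpm in the specification.

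**3. Simulation of the planned test.** From Section 8.2: 50 women less 10% = 45. Assumed, because the documents do not give them: two clinic pairs per woman (90 pairs, treated as independent), true FHR normal with SD 8 bpm and mean 135, 140, 145 or 150, and independent noise of SD 3 bpm on each method. Constant device bias was −20, −15, −10, +10, +15 or +20 bpm. That gives 4 × 6 = 24 settings, each tested with the exact two-sided McNemar test at 0.05. I re-ran the grid.

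| Mean FHR | Bias that escapes | Probability of detection |
|---|---|---|
| 135 | −10 | 11% |
| 135 | +10 | 11% |
| 140 | −10 | about 0% |
| 140 | −15 | 7% |
| 145 | −10 | 11% |
| 145 | −15 | 7% |
| 145 | −20 | about 1.5% |

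These are 7 of the 24 settings. In the other 17, detection is about 84% or more: for example 95% at mean 135 with −15, about 84% at mean 140 with −20, and 94.5% at mean 150 with −15.

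The reason is visible at mean 145. Flag agreement is 97% for an unbiased device and 96%, 95% and 92% for biases of −10, −15 and −20. At −10, about 0.039 × 90 = 3.5 discordant pairs are expected. The exact test needs at least six, all in one direction (2 × 0.5^6 = 0.031). At −20, discordant flags balance at about 4% each way, so the test has nothing to find.

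**4. Sensitivity.** With 45 pairs (one per woman), no measurement noise and reference mean 140, SD 10, detection is about 0% at −10, 3% at −15 and 45% at −20, against 56%, 99% and about 100% at +10, +15 and +20. The dependence on direction remains.

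**5. What the numerical differences would give.** Under the assumed noise, the SD of a difference is √(3² + 3²) = 4.24 bpm. With one pair per woman, the standard error of the mean bias is 4.24/√45 = 0.63, so the 95% CI is ±2.015 × 0.63 = ±1.3 bpm. If the SD were 10, it would be ±2.015 × 10/√45 = ±3.0 bpm. A bias of −10 bpm would be plain in either case. The 95% limits of agreement for an *unbiased* device would be ±1.96 × 4.24 = ±8.3 bpm, and each limit would carry a CI of about ±0.50 × 4.24 = ±2.1 bpm.

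**The case against.** The strongest case against has four parts.

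- **Accuracy is not a listed aim.** It appears in an introductory proposition in Section 1.0. It is not one of the numbered hypotheses or an objective in Section 5.1, and Section 8.2 makes SUS the primary outcome. Objective 1b covers the clinical usefulness of the readings, for which a flag is a reasonable measure. This stands. A reader might infer that the trial fails to test a stated objective, but the documents do not support that. The mismatch is between the data collected in Section 5.6, with the proposition in Section 1.0, and the analysis in Section 8.0.
- **Appendix E may contain the method.** It is cited for exactly this comparison and was not available. A reading rule or an agreement analysis there cannot be excluded, so the point is verified for Section 8.0 and the rest of the available text only. A reader might also infer that the numerical readings are thrown away. Nothing says so; they are simply given no numerical summary in Section 8.0.
- **The planned test often works.** It does, in 17 of the 24 settings. The inference that any error of 10 to 20 bpm would pass is wrong: a 20 bpm bias escapes in only one of eight settings.
- **The 110/160 limits have clinical meaning.** Agreed, and the flag should be kept.

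What remains is that Section 8.0 names a specific method that cannot show the size or direction of a numerical error, when data able to estimate mean bias are already collected.

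**Conclusion.** The point holds, as a cheap improvement. Section 8.0 compares FHR with standard care only through a 110/160 flag and McNemar's test, and states no analysis of MHR. The band arithmetic needs no assumptions: errors of 10 bpm are invisible in either direction over references of 120 to 150, and errors of 20 bpm over 130 to 140.

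The detection figures (about 11% or less in 7 of 24 settings, about 84% or more in 17) rest on an assumed mean, SD, noise and number of visits, and on treating repeated pairs from one woman as independent. The count of 7 in 24 describes a grid of settings. It is not the probability that a biased device would pass.

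A reader might also infer that the clinic pairs could verify the ±2 BPM specification reading by reading. They could not. With the assumed noise, even an unbiased device has limits of about ±8.3 bpm, and no section says that this trial will verify the specification. Mean bias can be estimated well; accuracy of a single reading cannot be tested this way.

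**What to change.** In Section 8.0:

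1. Make the main analysis of the clinic pairs the numerical difference, HeraBEAT session median minus clinic reading, separately for FHR and MHR. The median settles which value is used. Section 3.3 gives one value per second and Table 1 an automatic stop after 5 minutes of successful measurement, so a session can hold about 5 × 60 = 300 values.
2. Report mean bias with a 95% CI and Bland-Altman 95% limits of agreement, with woman as a random effect to allow for repeated visits.
3. Interpret the mean bias alongside the device specification. Report the limits descriptively, and say that they include noise in the clinic method and any delay between the two readings.
4. Keep the 110/160 flag as a secondary description.
5. If Appendix E already gives a reading rule or a comparison method, align Section 8.0 with it and cross-refer.

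The cost is some wording and a little extra analysis, with no new data. The drawback is that the limits will look wider than the specification, and the report must explain why.
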